10.4. Laboratory Evaluations

Blood samples are taken at Screening, Day 1, Day 7, Day 10, Day 14, then every 14 days as required, up to EoT and Follow-Up for the central evaluation of hematology, chemistry and urinalysis laboratory tests.

Summaries of laboratory data will be based on the Safety Population.

Continuous laboratory results for hematology, chemistry and urinalysis will be summarized, by treatment, at baseline, Day 7, Day 10, Day 14, and all further scheduled visits, up until EoT and Follow-Up. In addition, for post baseline visits, a summary will also be given for the change from baseline.

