15.8 Twelve-Lead Electrocardiogram

A 12-lead ECG will be obtained and evaluated locally by a physician for the presence of abnormalities at Screening and Baseline (Treatment Day 1), once between days 7 and 21, at EoT and at unscheduled visits, if applicable.

Heart rate, PR interval, QRS, QT and QTcF values will be recorded in the eCRF. Any clinically relevant abnormality will be recorded as AE accordingly and will be followed up to resolution/satisfaction.

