15.17 Safety Laboratory Tests

Safety laboratory tests (hematology, blood chemistry and urinalysis) will be performed at Screening and Baseline (Treatment Day 1), and on Treatment Days 7 and 14, at EoT and 6-Week FU. Electrolyte disturbances such as hypokalaemia, hypomagnesaemia and hypocalcaemia should be monitored and corrected, if necessary, prior to initiation and during voriconazole therapy. If clinically indicated, safety tests will be repeated every 14 days following Treatment Day 14 up to EoT, and at unscheduled visits. These may also be done more frequently as followup to a laboratory abnormality. If the subject is still receiving study drug by Day 42 (i.e., EoT has not occurred), a safety lab assessment should be conducted on Day 42 or on Day 56. Safety laboratory tests will be processed at a central laboratory. Procedures for collecting, storing, and shipping samples to the central laboratory are described in the study laboratory manual.
SCYNEXIS, Inc.	IND #107,521
PROTOCOL SCY-078-206	Version 5.0

Results from safety laboratory test by the central lab will be made available to the sites on an ongoing basis; however, the site should not relay on timely availability of these result to make medical decisions for subjects' care.

Additional laboratory tests should be collected and analyzed by the local laboratory, as needed, to make real-time medical decisions. Specifically, in line with voriconazole label

recommendations, serum transaminase levels, bilirubin levels, serum electrolytes (potassium, magnesium and calcium) and amylase and lipase should be monitored at initiation of voriconazole therapy (Day 1) and then weekly during the first month of treatment (Day 7, Day 14, Day 21 and Day 28). Monitoring frequency of these laboratory parameters may be reduced to monthly intervals during continued use of voriconazole if no clinically significant changes are noted.

The following laboratory parameters will be determined for all samples sent to the central laboratory:

Hematology

• White blood cell (WBC) count

Red blood cell (RBC) count

 Hemoglobin Hematocrit

- Platelet count
- Differential WBC count will include percentages for segmented neutrophils, lymphocytes, monocytes, eosinophils and basophils, and absolute counts for neutrophils, lymphocytes, atypical lymphocytes, monocytes, eosinophils and basophils.

Blood Chemistry

- Sodium
- Potassium
- Magnesium
- Calcium
- Alkaline Phosphatase
- Chloride
- Blood urea nitrogen (BUN)
- Creatinine

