- l. At Screening, at least one positive serum or BAL sample collected within 96 hours before enrollment must be available for all subjects. For subjects with a possible IPA, serum or BAL samples will be collected daily for a maximum Screening Period of 4 days (Days -4 to -1) until at least one positive GMI result (≥ 0.5 for serum and ≥ 1 for BAL) is reported. If a positive serum or BAL GMI test is reported after 4 days but no more than 7 days of mold-active antifungal treatment, the case will be discussed with the medical monitor to evaluate eligibility. If GMI results during the Screening period are negative, the subject will not be randomized and will be discontinued from the study.
- m. Samples for serum GMI assessments will be obtained within 2 hours before first dose of randomized treatment.
- n. Clinical safety laboratory assessments by the central laboratory will include hematology, blood chemistry and urinalysis. Additional laboratory tests should be collected and analyzed by the local laboratory, as needed, to make real-time medical decisions. Specifically, in line with voriconazole label recommendations, serum transaminase levels, bilirubin levels, serum electrolytes (potassium, magnesium and calcium) and amylase and lipase should be monitored at initiation of voriconazole therapy (Day 1) and then

Statistical Analysis Plan

Sponsor: Scynexis, Inc.; Protocol No.: SCY-078-206

Visit	Screening Period	Baseline(Treatment Day 1)	Treatment Day 3	Treatment Day 5	Treatment Day 7	Treatment Day 10	Treatment Day 14	Every 14 days during treatment ^a	EoT ^b	6-Week FU (6 weeks after EoT)	Unscheduled Visits
Days (allowable window)	Day -4 to Day -1 ^c	0	+ 1	+1	+1	+1	+1	± 2 days	± 1 day	± 2 days	
Procedure											

weekly during the first month of treatment (Day 7, Day 14 and Day 21, Day 28). Monitoring frequency of these laboratory parameters may be reduced to monthly intervals during continued use of voriconazole if no clinically significant changes are noted.

- o. If the subject is receiving study drug by Day 42 (i.e., EOT has not occurred), a safety lab assessment should be conducted on Day 42 or on Day 56.
- p. Voriconazole TDM will be conducted as per local standard practice and samples will be processed locally. All results available from locally conducted tests of voriconazole plasma concentrations, including those prior to Randomization, will be documented in the eCRF.

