10.5. Vital Signs

Vital signs include SBP, DBP, pulse rate, respiratory rate and body temperature, and are collected at Screening, Day 1 and EoT.

Temperatures captured in °F will be converted to °C using the formula:

$$\text{Temperature (in } ^\circ\text{C)} = 5/9 (\text{Temperature [in } ^\circ\text{F]} - 32).>$$

Vital signs will be summarized, by treatment, for the Safety Population at baseline and EoT. In addition, at EoT a summary will be given for the change from baseline.

10.6. 12-Lead ECG

A 12-lead ECG is collected at Screening, Day 1, Day 10 and EoT.

Summaries of ECG data will be based on the Safety Population.

Overall interpretation will be summarized, by treatment, at baseline, Day 10 and EoT.

ECG parameters, including heart rate, PR interval, RR interval, QRS interval and QTcF interval will be summarized, by treatment, at baseline, Day 10 and EoT. In addition, at Day 10 and EoT a summary will be given for the change from baseline.

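### SAP 10.4 tabulates central labs by arm at visits sampled only when clinically indicated, and at a Day 10 with no planned lab

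*SAP*

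**What the plan says.** **Labs, sampling.** Protocol 15.17 fixes central safety labs at Screening and Baseline, "and on Treatment Days 7 and 14, at EoT and 6-Week" follow-up. Beyond that, "If clinically indicated, safety tests will be repeated every 14 days following Treatment Day 14 up to EoT, and at unscheduled visits". There is one exception: for a subject still on study drug at Day 42, "a safety lab assessment should be conducted on Day 42 or on Day 56". SAP 3.8 carries the same rule in footnote o of Table 1: "If the subject is receiving study drug by Day 42 (i.e., EOT has not occurred), a safety lab assessment should be conducted on Day 42", with Day 56 given as the alternative. The safety-lab row in both schedules (Protocol Table 4, SAP Table 1) is blank at Day 10 and conditional at the 14-day visits.

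**Labs, analysis.** SAP 10.4 describes central sampling after Day 14 as being on an as-needed basis, but adds a Day 10 sample. It then summarises values and changes from baseline by treatment "at baseline, Day 7, Day 10, Day 14, and all further scheduled visits, up until EoT and Follow-Up".

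**Local labs.** Protocol 15.17 also states: "Additional laboratory tests should be collected and analyzed by the local laboratory, as needed, to make real-time medical decisions". It names transaminases, bilirubin, electrolytes, amylase and lipase, weekly to Day 28 and possibly monthly after that. SAP 10.4 speaks only of central evaluation.

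**ECG.** Protocol 15.8 requires an on-treatment ECG "once between days 7 and 21, at EoT and at unscheduled visits, if applicable". SAP 10.6 states: "A 12-lead ECG is collected at Screening, Day 1, Day 10 and EoT", and summarises the on-treatment reading as Day 10. SAP 6.1 and 6.4 assign data to nominal visits without windows, and SAP 6.1 keeps repeat and unscheduled assessments out of the summaries.

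**The concern.** A by-visit table of means invites the reader to treat each row as describing the arm at that time. That holds where every subject on treatment is due a sample. Where a sample is taken because someone judged it necessary, the row describes the subjects who were judged to need it, and the two arms may be sampled for different reasons and at different rates. Change from baseline does not cure this, because the selection acts on the post-baseline visit.

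The point matters here because safety and tolerability are the primary objective, and SAP section 10 bases safety on labs and ECG as well as adverse events. The by-visit tables are also the only laboratory summaries the SAP specifies. Protocol 19.6.2 promises shifts against the reference range and a summary of events of clinical interest, but SAP 10.3 and 10.4 contain neither, so no other laboratory table offsets the weakness.

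**Working it through.** No power, alpha or effect size is stated, so there is no planned figure to reproduce. The check sets the tabulated rows against the mandated samples and then looks at the denominators.

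**1. Rows against mandated samples** (subject treated for the full 13 weeks, 91 days)

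| SAP 10.4 row | Central lab in the schedule |
|---|---|
| Day 7 | mandated |
| Day 10 | none planned |
| Day 14 | mandated |
| Day 28 | if clinically indicated |
| Day 42 | mandated here or at Day 56 |
| Day 56 | mandated here or at Day 42 |
| Day 70 | if clinically indicated |
| Day 84 | if clinically indicated |

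Rows tabulated: 3 (Days 7, 10, 14) + 5 (Days 28, 42, 56, 70, 84) = 8. Mandated samples for one subject: 2 (Days 7, 14) + 1 (Day 42 or 56) = 3. After Day 14, 1 of the 5 rows is mandated. Baseline, EoT and 6-week follow-up are mandated in addition. A subject treated for less time reaches fewer rows, but Day 10 and Day 28 have the same status.

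**2. Denominator at Day 28** (illustration)

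SAP 3.4 gives 22 randomised, 11 per arm. Assume all 11 are still on treatment and each independently has an indicated sample with probability p. The documents do not give p, so a range is shown. Expected n = 11p, and P(n ≤ 2) is the exact binomial lower tail.

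- p = 0.10: n = 1.1, P(n ≤ 2) = 0.91
- p = 0.25: n = 2.75, P(n ≤ 2) = 0.46
- p = 0.50: n = 5.5, P(n ≤ 2) = 0.03

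**3. Split of the late mandated sample** (illustration)

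Assume all 11 are on drug at Day 42 and a share s is sampled then, the rest at Day 56, with no extra indicated samples.

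- s = 0.3: 3.3 at Day 42 and 7.7 at Day 56
- s = 0.5: 5.5 and 5.5
- s = 0.7: 7.7 and 3.3

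Pooled, the same record has all 11.

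**4. Direction of the bias**

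Let S indicate being sampled, Y the laboratory value and π = P(S = 1) within an arm. Then E[Y | S = 1] − E[Y] = Cov(S, Y)/π. The bias in the arm difference is this term for one arm minus the term for the other. Neither covariance nor sampling rate is known, so the sign is not determined.

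**5. ECG timing**

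Days 7 to 21 inclusive are 21 − 7 + 1 = 15 permitted days. Scheduled visits in that span, with their one-day windows, cover Days 7–8, 10–11 and 14–15, that is 6 days. The other 15 − 6 = 9 days (9, 12, 13, 16 to 21) fall in no scheduled visit window. An ECG on one of those days complies with the protocol but could be logged as unscheduled.

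**The case against.** The best defence is that little rests on these tables. The primary endpoint counts adverse events, discontinuations and deaths (SAP 4.1). Clinically significant laboratory abnormalities are recorded as adverse events (Protocol 17.1), as are clinically relevant ECG findings (15.8). Events of clinical interest, defined by QTc and by ALT/AST, go on the adverse event form (17.3). Each row will show its n, no test is planned, and all relevant data are listed. This stands, and it limits the problem to descriptive safety tables.

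Several stronger readings are tempting, and the documents do not support them.

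- *Everything central after Day 14 is conditional.* It is not: the Day 42/56, EoT and follow-up labs are due regardless of indication.
- *The conditional rows hold only abnormal results, so the arm sampled more looks worse.* Clinical indication is not the same as an abnormal result. Nor does more sampling imply a worse mean. As an assumed example, three subjects sampled at ALT 150 U/L give a mean of 150. Sampling six more at 30 gives (3 × 150 + 6 × 30)/9 = 70.
- *Most on-treatment ECGs fall outside the Day 10 row.* The only on-treatment ECG cell sits in the Day 10 column with the Days 7–21 footnote, it is due in every subject, and the SAP applies no windows. Day 10 is most naturally the nominal label for that ECG. Treating the visit's one-day window as an analysis filter (2 of 15 days) goes against SAP 6.4. An ECG drops out only if it is logged as unscheduled, which depends on eCRF design that is not in the documents.

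**Conclusion.** The laboratory point holds. SAP 10.4 tabulates a Day 10 lab that no schedule plans. It presents Days 28, 70 and 84 as ordinary visits although those samples are indication-driven, and it divides the one late mandated sample between two rows. In total, 3 of 8 tabulated on-treatment days carry a mandated sample for a given subject. With about 11 per arm, the Day 28 row may hold one to six subjects per arm under the assumed sampling rates of 10% to 50%. The actual rate is unknown, and the direction of any distortion cannot be stated. The Baseline, Day 7, Day 14, EoT and follow-up rows are sound in this respect, and the primary endpoint is not touched.

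The ECG point is smaller. It is a matter of labelling, with a risk that a compliant reading is excluded if it was entered as unscheduled.

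This should be corrected in the SAP, but it does not threaten the study's main conclusion.

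**What to change.** **SAP 10.4.** Limit by-visit summaries to Baseline, Day 7, Day 14, one pooled Day 42/56 record, EoT and follow-up. Delete Day 10. List the indication-driven samples, and use them otherwise only in a summary of each subject's worst on-treatment value. Add local results to that summary, as multiples of the local upper limit of normal, only if both results and ranges are already in the eCRF. This condition matters: Protocol 15.17 does not explicitly ask for local safety labs to be entered, whereas 15.15, 15.16 and 15.18 do so for local galactomannan, β-D-glucan/PCR and voriconazole levels. Section 18.1 is general, and 18.3 places normal ranges in site files. With enrolment stopped, retrospective collection would be a different undertaking.

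**SAP 10.6.** Define the Day 10 row as the single on-treatment ECG taken on Days 7 to 21, whatever its visit label, and state that this overrides the exclusion of unscheduled assessments in SAP 6.1.

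**Cost.** SAP wording and modest programming. There will be fewer by-visit rows, and the worst-value summary still depends on how often a subject is sampled, so it should report the number of samples per subject by arm.

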10.5. Vital Signs

Vital signs include SBP, DBP, pulse rate, respiratory rate and body temperature, and are collected at Screening, Day 1 and EoT.

Temperatures captured in °F will be converted to °C using the formula:

$$\text{Temperature (in } ^\circ\text{C)} = 5/9 (\text{Temperature [in } ^\circ\text{F]} - 32).>$$

Vital signs will be summarized, by treatment, for the Safety Population at baseline and EoT. In addition, at EoT a summary will be given for the change from baseline.

10.6. 12-Lead ECG

A 12-lead ECG is collected at Screening, Day 1, Day 10 and EoT.

Summaries of ECG data will be based on the Safety Population.

Overall interpretation will be summarized, by treatment, at baseline, Day 10 and EoT.

ECG parameters, including heart rate, PR interval, RR interval, QRS interval and QTcF interval will be summarized, by treatment, at baseline, Day 10 and EoT. In addition, at Day 10 and EoT a summary will be given for the change from baseline.

10.7. Physical Examination

A general physical examination is done at Screening, Day 1, Day 14, Day 28, Day 42, Day 56, Day 70, Day 84, EoT and at Follow-Up.

Physical examination results will be summarized, by treatment, for the Safety Population.

11. Interim Analyses

The protocol planned for the performance of an interim analysis. However, there is no interim analysis since the study was stopped after enrolment of 22 subjects, due to patient recruitment challenges..

12. Changes from Analysis Planned in Protocol

There are currently no deviations from the analyses planned in the protocol. Enrollment into the study was stopped after 22 subjects were randomized because of the subject recruitment challenges and feasibility to enrol the planned sample size of 60 subjects.

13. Programming Considerations

All tables, figures, listings (TFLs), and statistical analyses will be generated using SAS for Windows, Release 9.4 or higher (SAS Institute Inc., Cary, NC, USA). Computer-generated table, listing and figure output will adhere to the following specifications.

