19.0 Analytical Plan

All statistical processing will be performed using SAS[®] version 9.3 or later, unless otherwise stated.

Descriptive statistics (i.e., number of subjects, mean, standard deviation, median, minimum, maximum) will be presented for all continuous variables; number and percentage of subjects will be presented for categorical variables. For parameters measured over time, observed data and changes from baseline will be described for each time point.

When feasible, based on adequate sample size sub-group analyses including by gender and by underlying condition will be conducted.

A Statistical Analysis Plan (SAP) describing all statistical analyses in detail will be provided as a separate document.

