19.6.2 Safety Analyses

All safety analyses will be conducted using the ITT/safety population; all safety variables will be listed.

The incidence and severity of TEAEs and SAEs and their relationship to treatment will be summarized. AEs will be coded using the Medical Dictionary for Regulatory Activities (MedDRA) Version 19.1 or higher and presented by system organ class and preferred term.

Early discontinuation of study drug treatment will be presented and will include the reasons for and timing of such discontinuations.

Prior and concomitant medications will be summarized; medications will be classified based on the World Health Organization's Drug Dictionary terminology.

Abnormal physical examinations will be listed. Laboratory evaluations will be summarized as observed values and changes from Baseline; shifts with respect to the laboratory reference range will be summarized. Events of clinical interest will be summarized.

Vital signs and ECG evaluations will be summarized as observed values and changes from Baseline.

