 - 10.2. Treatment Compliance32
 - 10.3. Adverse Events.....32
 - 10.4. Laboratory Evaluations.....34
 - 10.5. Vital Signs34
 - 10.6. 12-Lead ECG.....34
 - 10.7. Physical Examination34
- 11. Interim Analyses35
- 12. Changes from Analysis Planned in Protocol.....36
- 13. Programming Considerations.....37
 - 13.1. General Considerations.....37
 - 13.2. Table, Listing, and Figure Format37
 - 13.2.1. General.....37
 - 13.2.2. Headers37
 - 13.2.3. Display Titles.....38
 - 13.2.4. Column Headers38
 - 13.2.5. Body of the Data Display.....38
 - 13.2.6. Footnotes40
- 14. Appendices.....42
 - 14.1. Treatment Outcome42
 - 14.2. PopPK analysis plan43

1. Glossary of Abbreviations

Abbreviation	Description
ACM	All-Cause Mortality
AE	Adverse Event
ATC	Anatomical Therapeutic Chemical
AUC	Area Under the Concentration-Time Curve
AUC _{0-inf}	Area under the concentration-time curve extrapolated to infinity
AUC _{0-last}	Area under the curve from the time of dosing to the last measurable concentration
BMI	Body Mass index
CI	Confidence Interval
CL/F	Apparent clearance
C _{max}	Maximum Concentration
CT	Computed Tomography
DRC	Data Review Committee
ECG	Electrocardiogram
EoT	End of Treatment
FU	Follow-Up
GMI	Galactomannan Index
λ_z	Terminal elimination phase rate constant
HCT	Hematopoietic Cell Transplantation
HM	Hematological Malignancy
ICU	Intensive Care Unit
IPA	Invasive Pulmonary Aspergillosis
ITT	Intent-to-Treat
IV	Intravenous
Max	Maximum
MedDRA	Medical Dictionary for Regulatory Activities
Min	Minimum
MITT	Modified Intent-to-Treat
NG	Nasogastric
PEG	Percutaneous Endoscopic Gastrostomy

Statistical Analysis PlanSponsor: Scynexis, Inc.; Protocol No.: SCY-078-206

Abbreviation	Description
PK	Pharmacokinetics
PP	Per Protocol
PT	Preferred Term
QTc	Corrected QT Interval
SAE	Serious Adverse Event
SAP	Statistical Analysis Plan
SD	Standard Deviation
SOC	System Organ Class
SOP	Standard Operating Procedure
TEAE	Treatment Emergent Adverse Event
T _{max}	The first time to maximum observed concentration sampled during a dosing interval
TFL	Table, Figure and Listing
WHODD	World Health Organization Drug Dictionary

2. Purpose

The purpose of this statistical analysis plan (SAP) is to ensure that the data listings, summary tables and figures which will be produced, and the statistical methodologies that will be used, are complete and appropriate to allow valid conclusions regarding the study objectives.

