9.2. PK Concentration

The summary statistics of plasma concentrations will be presented per treatment (ibrexafungerp, voriconazole), PK Day (Pre-first dose, Day 1, Day 7 and Day 14) and by time interval (pre-dose, 2-4 and 6-8 hours post dose), and BLQ concentration values should be set to 0. All concentration values presented as BLQ and the number of BLQs (ie, n below the lower limit of quantitationLLOQ) for each time interval will be listed as reported.

10. Safety

The population used for safety analyses will be the Safety Population. Safety will be assessed on the basis of AEs, clinical laboratory data, vital signs, ECG parameters and physical examinations

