10.3. Adverse Events

Adverse events will be coded into SOCs and PTs using the MedDRA 26.0 .

If the relationship to a study drug is missing then in the summary tables the AE will be classified as related. Similarly, missing severity will be classified as severe in the summary tables.

Treatment-related AEs will be those with relationship to either ibrexafungerp or voriconazole of related.

Summary tables of AEs will be based on treatment emergent adverse events (TEAEs).

A TEAE is defined as any event not present prior to the initiation of the study treatment, or any event already present which worsens either in intensity or frequency following the exposure to the study treatment.

AEs with incomplete start dates will be considered as TEAE if:

- Day and month are missing and the year is equal to or after the year of the first dose date
- Day is missing and the year is after the year of the first dose
- Day is missing and the year is equal to the year of the first dose date and the month is equal to or after the month of the first dose date
- Year is missing
- Complete start date is missing.

For summaries by SOC and PT, a subject will be counted once at the SOC level and once at each PT within the SOC level. For summaries by SOC, PT and maximum severity, a subject will be counted once at the highest severity for which an event occurred at the SOC level and the highest severity for each unique PT within that SOC level. Therefore, subjects may only contribute once to each PT and once to each SOC level.

An overall summary of TEAEs will be provided showing the number and percentage of subjects reporting TEAEs, treatment-related TEAEs, TEAEs with severe severity, TEAEs leading to withdrawal of study treatment, serious TEAEs and treatment-related serious TEAEs, TEAEs leading to Death.

The following TEAE tables will also be provided:

- A summary of TEAEs overall and by SOC and PT
- A summary of treatment-related TEAEs overall and by SOC and PT
- A summary of TEAEs by maximum severity, overall and by SOC and PT
- A summary of TEAEs leading to withdrawal of study treatment, overall and by SOC and PT
- A summary of serious TEAEs, overall and by SOC and PT
- A summary of treatment-related serious TEAEs, overall and by SOC and PT
- A summary of TEAEs leading to Death, overall and by SOC and PT

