The above summaries will show the number and percentage of subjects reporting events in the respective categories. All summaries will be by treatment group. Only the TEAEs will be included in the summary tables, however all AEs will be included in the listings.

Listings will be provided for all AEs, AEs leading to study treatment withdrawal and SAEs. TEAEs will be flagged in the listings.

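### The SAP specifies neither the event-of-clinical-interest summary nor the laboratory shift summary that the protocol commits to, yet SAP 12 declares no deviations

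*SAP*

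**What the plan says.** Protocol 19.6.2, repeated in the synopsis under Safety Analyses, states: "shifts with respect to the laboratory reference range will be summarized. Events of clinical interest will be summarized". Protocol 17.3 defines ECIs by five criteria (one on QTc, four on ALT or AST) and requires each to be recorded as an ECI on the AE eCRF. Protocol 19.0 gives the SAP the task of setting out the analyses: "A Statistical Analysis Plan (SAP) describing all statistical analyses in detail will be provided as a separate document". SAP 2 gives its own purpose as ensuring that "the data listings, summary tables and figures which will be produced, and the statistical methodologies that will be used, are complete and appropriate" for valid conclusions.

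The SAP's safety section opens with "Safety will be assessed on the basis of AEs, clinical laboratory data, vital signs, ECG parameters and physical examinations". SAP 10.3 then specifies an overall TEAE summary, seven TEAE tables and three listings (all AEs, AEs leading to treatment withdrawal, SAEs), adding that "TEAEs will be flagged in the listings". SAP 10.4 specifies continuous laboratory results by visit and then: "In addition, for post baseline visits, a summary will also be given for the change from baseline". SAP 10.6 summarizes ECG parameters, their change from baseline and the overall interpretation. SAP 12 states "There are currently no deviations from the analyses planned in the protocol" and otherwise mentions only that enrollment stopped at 22 subjects.

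**The concern.** The protocol made two specific promises about safety output in a trial whose primary objective is safety. The document meant to carry them out mentions neither and then certifies that nothing has changed. A reader who relies on SAP 12 has no reason to look for a gap, and a programmer working from SAP 10 has no instruction to fill it.

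The outputs that remain do not do the same job. In the SOC and PT tables "a subject will be counted once at the SOC level and once at each PT within the SOC level". One ECI criterion requires, in the same subject, ALT or AST above 3 x ULN together with bilirubin above 2 x ULN or INR above 1.5. No PT row counts that combination. Likewise, means and mean changes of ALT do not show how many subjects moved from within to above the reference range.

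**Working it through.** The claim concerns text, and the plan has no figure of its own to reproduce, so the first step sets commitments beside specifications.

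| Protocol commitment (19.6.2, synopsis) | What the SAP specifies | Declared in SAP 12? |
|---|---|---|
| Summary of ECIs | 10.3: one overall TEAE summary, seven TEAE tables, three listings, none for ECIs. 10.6: no count against the QTc ECI thresholds | No |
| Summary of laboratory reference-range shifts | 10.4: continuous values and change from baseline, no low/normal/high classification | No |

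The SAP's section 10 contents and its abbreviation list have no ECI or shift entry either. So two of the two commitments are unspecified and neither omission is declared.

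Second step: is either commitment conditional? The protocol qualifies other analyses. The exploratory objectives (9.3) depend on what the data allow, the efficacy subgroups (19.7.2) on sufficient data, and the sub-group analyses in 19.0 on adequate sample size. The two sentences in 19.6.2 carry no such condition, so stopping at 22 subjects does not release them.

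Third step: can the specified outputs stand in for the missing ones? Two illustrations follow, with **assumed** values and 11 subjects per arm (SAP 3.4). They show what is possible, not what is likely.

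*Shifts, ALT, baseline to EoT only.* Assume both arms start with 0.3 x ULN in 3 subjects, 0.8 in 5 and 1.3 in 3 (all below the entry limit of 5 x ULN), with 0.3 and 0.8 counted as normal.

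- Arm X: three subjects go from 0.8 to 1.3 and three from 1.3 to 0.8.
- Arm Y: three go from 0.3 to 0.8 and three from 0.8 to 0.3.
- In both arms, at baseline and at EoT: mean = (3 × 0.3 + 5 × 0.8 + 3 × 1.3)/11 = 8.8/11 = 0.80; SD = √(6 × 0.25/10) = 0.39; median 0.8; range 0.3 to 1.3.
- Change in both arms: +0.5 in three, −0.5 in three, 0 in five; mean 0; SD = √(6 × 0.25/10) = 0.39; median 0; range −0.5 to +0.5.

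The baseline, EoT and change statistics are therefore the same in both arms, while the shifts differ:

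| Shift, baseline to EoT | Arm X | Arm Y |
|---|---|---|
| Normal to high | 3/8 (37.5%; exact 95% CI 8.5% to 75.5%) | 0/8 (0% to 36.9%) |
| High to normal | 3/3 | 0/3 |

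Arm X has three moves up and three down, so the example does not show that X is worse. It shows that the specified statistics cannot tell the two patterns apart. It says nothing about Day 7, Day 14 or the other visits.

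*ECIs.* Assume 3 subjects in each arm have the same ALT preferred term and one of them, in one arm, meets an ECI criterion. The PT row reads 3/11 (27.3%) in both arms. An ECI row would read 1/11 (9.1%; exact 95% CI 0.2% to 41.3%) against 0/11 (0% to 28.5%). In both examples the intervals overlap, so the counts are descriptive.

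**The case against.** The best defence is that the SAP is silent and withdraws nothing. SAP 12 could be read as leaving the protocol's analyses in force, and table shells, which are not among the documents, might contain both outputs. This stands in part. A reader might infer that the sponsor has dropped the two summaries; the documents do not show that. They show that the SAP neither specifies them nor declares their absence. The defence does not rescue SAP 12, because Protocol 19.0 places the detailed description of all analyses in the SAP. The SAP 2 purpose statement adds less: it aims at outputs sufficient for valid conclusions and does not claim to list every table.

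A second defence is that nothing is hidden. SAP 6.1 lists all relevant subject data, and repeat and unscheduled results are listed too. ECIs sit on the AE eCRF and so fall within the listing of all AEs. A severe, serious or fatal liver event, or one leading to withdrawal, would also appear in the corresponding TEAE table. With 22 subjects a reader could count ECIs and shifts by hand. All of this stands. It is also tempting to infer from SAP 10.3 that the AE listings would identify TEAEs only and not ECIs; the text does not say so. But the protocol promised summaries as well as listings.

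A third defence is that the protocol never promised an ECI count per criterion, nor shifts at every visit. That is correct: a total ECI count by arm would meet the wording, and so would a shift summary at stated visits.

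**Conclusion.** The point holds, and the SAP 12 statement is wrong as written. Two unconditional protocol commitments on safety reporting have no counterpart in the SAP, and neither omission is declared.

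The consequence is modest. A reader might infer that the primary endpoint is compromised or that safety data are lost. Neither follows. TEAEs, drug-related AEs, discontinuations due to AEs and deaths do not depend on these summaries, and the underlying records remain in the listings. What is missing is a specified between-arm ECI count and a specified view of who crossed a reference limit, both descriptive at this sample size. The finding rests on the SAP text alone and would be softened, though SAP 12 would still need correcting, if the table shells turned out to include these outputs. It does not rest on the numerical illustrations, whose inputs are assumed.

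**What to change.** - **SAP 10.3:** add the number and percentage of subjects with any ECI by arm, taken from the ECI records on the AE eCRF. Break it down by Protocol 17.3 criterion only if the eCRF stores which criterion was met; the documents do not say whether it does.
- **SAP 10.4:** add a low/normal/high reference-range shift summary by arm from the central laboratory data, at least baseline to EoT, and state any further scheduled visits. Settle the visit set at the same time, since SAP 10.4 names Day 10 but the schedule of procedures marks no safety laboratory at Day 10.
- **SAP 12:** correct the statement on deviations, or declare and justify whichever summary stays omitted.

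Optional: a separate ECI listing, shifts at every scheduled visit, and a baseline-to-worst-value shift table. The last would need a stated exception to SAP 6.1, which keeps repeat and unscheduled results out of summaries.

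The cost is two tables or table sets (the shift summary covers each analyte with a reference range) and one corrected sentence. No new data collection is required.
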